The collected blood will be expanded ex-vivo by aAPCs. The expansion will take 14 days. The process can generate 2.5×10^9 to 1×10^{10} cells which will be formulated for infusion in 100-500 mL of human serum albumin infusion buffer. Cells for later additional infusions may be cryopreserved.

Patients will receive a single infusion of ex-vivo expanded autologous T-Cells. Optimal dose will be 1×10^{10} activated T cells (+/- 20%), however for patients who cannot achieve that dose, a lower dose of activated T cells that meets release criteria may be infused at the discretion of the Principal Investigator.

Additionally, patients who have been previously treated on study, and subsequently need additional infusions may be retreated with previously cryopreserved expanded cells at the same or lower dose level. Retreatment will occur 6-12 months after the first infusion as long as no DLT was noted with the first infusion. These patients will be only followed for toxicity. Patients who have previously experienced DLT will be removed from the study and will not be eligible for retreatment.

Packaging and Administration

The T cells will be administered via intravenous infusion over 20-30 minutes without a leukocyte filter.

Autologous co-stimulated T-cell infusion

1. Co-stimulated T-cells will be infused at a dose of approximately 1×10^{10} (+/-20%). If optimal cell dose of 1×10^{10} (+/-20%).) is not achieved, a lower dose of activated T cells that meets release criteria may be infused at the discretion of the Principal Investigator.
2. Patients will receive premedication with Acetaminophen 650 mg PO and/or diphenhydramine 25-50 mg IV at least 30 minutes prior to infusion.
3. Additional orders: Acetaminophen 650 mg PO q4h for temperature > 38°, diphenhydramine 25 mg IVPB q3-4h prn and meperidine 25 mg IVPB q 2h prn for chills (if chills persist inform MD). Anaphylaxis precautions: Following drugs should be available at bedside: 3cc epinephrine 1:1000, diphenhydramine 25 mg IV and hydrocortisone 100 mg IV. In the event of a severe allergic reaction (e.g., anaphylaxis, bronchospasm, hypotension) or serious adverse reaction (i.e., cardiac failure, respiratory failure, severe nausea and vomiting) to the T Cell therapy, the infusion of the autologous T Cells will be stopped immediately and the patient will be provided with the supportive care deemed necessary by the physician and medical staff at the clinic.

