4. Optional Procedure: With the patient's consent, if the patient cannot receive the co-stimulated T cells, the cells will remain cryopreserved in the Stem Cell Laboratory indefinitely. The patient can receive the cells at a later date. If the patient's physician feels that the patient will no longer benefit from the cells,

the cells may be used for research or discarded. If the patient refuses, the cells will be destroyed.

Study Enrollment:

The study population for this research will consist of participants from:

Only at MDACC

Estimated Accrual:

Total Accrual at MDACC:	40
Estimated monthly accrual at MDACC:	1

Accrual Comments:

The sample size of 40 patients was chosen for logistical reasons.

Is this an NCI-Cancer Therapy Evaluation Protocol (CTEP)? No

Is this an NCI-Division of Cancer Prevention Protocol (DCP)? No

Statistical Considerations:

Overview

This is a phase II trial of infusion of autologous T cells for immune restoration in patients with CLL. The primary scientific goal is to determine the feasibility and safety of this procedure. A total of 40 patients will receive T cell infusions. Endpoint evaluation will be at day +90 after the co-stimulated T cell infusion.

Sample Size

In this trial, the sample size of 40 patients was chosen for logistical reasons. With 40 patients, a 95% confidence interval around the success rate will be no wider than 32%.

Primary Endpoint

Success will be defined as achievement of a target activated T-cell dose of $1 \times 10^8 \pm 20\%$ and the lack of dose limiting toxicity (DLT).

For this trial DLT is defined as:

- Any grade 4 or higher non-hematologic toxicity or grade 3 or 4 allergy/immunology toxicity;
- Allergic reaction or urticaria grade 3 or higher (CTC v4.03 CTCAE) by +90 days after T cell infusion;
- Grade 2 or greater autoimmune phenomena; or,
- Grade 4 or higher hematologic toxicity (with the exception of any preexisting AE due to prior treatment or due to disease) deemed related to T cells and occurring by day +90 after T cell infusion.

Feasibility is defined as achievement of the target T cell dose ($1 \times 10^8 \pm 20\%$) without DLT in > 50% of patients enrolled.

Safety Monitoring

Any death due to the infusion of co-stimulated T-Cell product itself and not disease progression will be considered unacceptable and the study will be stopped. If the study is not terminated early, it will continue

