until all patients have been treated with co-stimulated T Cells and completed all follow up evaluations.

In addition, we will use a Bayesian sequential monitoring rule to monitor the primary endpoint of the study. If there is a high probability that the overall success rate is less than 50%, enrollment into the trial will be stopped. We will enroll a minimum of 6 patients onto the study before stopping. We will use the following criteria: we will stop enrollment if at any time during the course of the trial:

$\Pr [\text{90-day success rate} > 0.50 \mid \text{data}] < 0.025$

That is, if we determine that there is a less than 2.5% chance that the 90-day success rate is greater than 50%, accrual will be stopped. We assume a beta (1, 1) prior distribution for the success rate, which has a mean of 0.50 corresponding to the target success rate. Stopping boundaries corresponding to this probability criterion are to terminate accrual if:

If there are this many patients accrued	Stop the trial if this number of patients meet criteria for success
6-7	0
8-10	0-1
11-13	0-2
14-15	0-3
16-18	0-4
19-21	0-5
22-23	0-6
24-26	0-7
27-28	0-8
29-31	0-9
32-33	0-10
34-35	0-11
36-38	0-12
39	0-13
40	Always Stop

This stopping rule was chosen to assure that the probability that the trial will stop early would be approximately 10% if the true success rate was 50%. The operating characteristics of this rule are shown in the table below.

We will enroll 3 patients and then wait till all 3 have reached +90 days without DLT before enrolling more patients. At that time point 3 additional patients will be enrolled and we will wait till they have all reached

+90 days and without DLT before enrolling the remaining patients.

Operating Characteristics for Success Monitoring Rule

If the true 90-day success rate is...	Early Stopping Probability	Achieved Sample Size		
		25th percentile	50th percentile	75th percentile
0.3	0.833	8	16	32
0.4	0.413	19	40	40
0.5	0.108	40	40	40
0.6	0.018	40	40	40
0.7	0.002	40	40	40

The monitoring rules will be assessed by the study team with assistance as necessary from the Department of Biostatistics at MD Anderson Cancer Center.

Secondary Analyses

Immune reconstitution: We will assess the percentages and absolute values of CD3+, CD4+, CD8+ and CD4/CD8 ratio and report these at each time point along with 95% confidence intervals. In addition, immune reconstitution will be compared at each time point.

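### The primary endpoint scores dose against 1×10^8 cells while the treatment plan gives 1×10^10, so success does not show whether the planned dose was reached

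*Combined protocol and SAP*

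**What the plan says.** **Statistical Considerations, Primary Endpoint.** A patient is a success on "achievement of a target activated T-cell dose of $1 \times 10^8 \pm 20" percent, together with no DLT. The same section closes with "Feasibility is defined as achievement of the target T cell dose ($1 \times 10^8 \pm 20\%$) without DLT in > 50% of patients enrolled".

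**Proposed Treatment/Study Plan.** "Optimal dose will be 1×10^{10} activated T cells (+/- 20" percent). The sentence goes on: "however for patients who cannot achieve that dose, a lower dose of activated T cells that meets release criteria may be infused", at the investigator's discretion and with no numeric floor. On manufacturing: "The process can generate 2.5×10^9 to 1×10^{10} cells".

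**Autologous co-stimulated T-cell infusion.** "Co-stimulated T-cells will be infused at a dose of approximately 1×10^{10} (+/-20" percent), followed by a fallback that begins "If optimal cell dose of 1×10^{10} (+/-20%).) is not achieved".

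**Safety Monitoring.** The Bayesian rule runs on this success endpoint: "if we determine that there is a less than 2.5% chance that the 90-day success rate is greater than 50%, accrual will be stopped".

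The endpoint section therefore gives 1×10^8 twice, and the treatment sections give 1×10^10 three times.

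**The concern.** The two figures differ 100-fold and their ±20% windows do not overlap. Each is used consistently within its own part of the document, so a single misprint or text-extraction slip is an unlikely explanation. No per-kilogram unit, stated minimum or 1×10^8 dose level connects them.

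One definition of success supports three things: the primary endpoint, the more-than-50% feasibility conclusion and the stopping rule. If the dose part is met by practically any product that can be infused, the trial could be declared feasible, and the rule could stay silent, with few or no patients having reached 1×10^10. A patient given a much lower discretionary dose would score the same as one given the planned dose. With the conflict unresolved, two analysts could also score the same patient in opposite ways.

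**Working it through.** **1. The plan's own figures.** The rule stops when Pr(p > 0.50 | data) < 0.025 under a beta(1, 1) prior. After x successes in n patients the posterior is Beta(1+x, 1+n−x). The resulting boundaries match the printed ones for every n from 6 to 39. An exact binomial recursion, with a look after each patient from 6 to 39, gives:

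| True success rate | Printed early stopping | Recomputed |
|---|---|---|
| 0.3 | 0.833 | 0.833 |
| 0.4 | 0.413 | 0.413 |
| 0.5 | 0.108 | 0.108 |
| 0.6 | 0.018 | 0.018 |
| 0.7 | 0.002 | 0.002 |

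The rule is computed correctly. The problem is what enters it as a success.

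**2. Dose windows against the stated yield (2.5×10^9 to 1×10^10).**
- Endpoint target: 1×10^8 ±20% = 0.8×10^8 to 1.2×10^8.
- Treatment plan: 1×10^10 ±20% = 0.8×10^10 to 1.2×10^10.
- Lowest yield over the endpoint's lower limit: 2.5×10^9 / 0.8×10^8 = 31.
- Lowest yield over its upper limit: 2.5×10^9 / 1.2×10^8 = 21.

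**3. Printed target read as a threshold.** This is the more plausible reading, because the treatment plan speaks of not achieving the dose only when a patient falls short of it. Every lot in the stated range passes. Feasibility is taken over enrolled patients, so

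success rate = share infused × (1 − DLT rate).

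The shares infused and DLT rates below are assumptions.

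| Share infused | DLT rate | Success rate | Early stopping (Bayesian rule alone) |
|---|---|---|---|
| 1.0 | 0.30 | 0.70 | 0.002 |
| 0.9 | 0.20 | 0.72 | 0.001 |
| 0.8 | 0.30 | 0.56 | 0.038 |

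None of these depends on how many patients received 0.8×10^10 or more.

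**4. Target of 1×10^10 ±20%.** Within the stated range only yields of 0.8×10^10 to 1.0×10^10 qualify. The plan gives no yield distribution, so two are assumed, and lot yield is taken as the dose given.
- Uniform: (1.0 − 0.8)×10^10 / (1.0 − 0.25)×10^10 = 0.2/0.75 = 0.267.
- Log-uniform: ln(1.25)/ln(4) = 0.161.

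| Yield assumption | DLT rate | Success rate | Early stopping |
|---|---|---|---|
| Uniform | 0 | 0.267 | 0.92 (median sample size 14) |
| Uniform | 0.10 | 0.240 | 0.96 |
| Uniform | 0.20 | 0.213 | 0.99 |
| Log-uniform | 0 | 0.161 | 0.999 (median sample size 8) |

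**5. Printed target read as a literal two-sided window.** A patient given exactly the planned 1×10^10 lies above 1.2×10^8 and is a non-success. After 0 successes in 6 patients the posterior is Beta(1, 7), and Pr(p > 0.5) = 0.5^7 = 0.0078 < 0.025, so accrual stops at the first look.

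**The case against.** The conflict in the text is not disputed. The best case on the other side concerns its consequence.

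- **A deliberate lower bar.** The treatment plan calls 1×10^10 optimal and allows a lower dose that meets release criteria. The primary objective is feasibility and safety of infusing activated T cells, without naming a dose. Counting a safe lower-dose infusion as a success would fit that. But the endpoint section calls 1×10^8 a target, not a minimum, and gives it the same ±20% tolerance as the planned dose. A floor would have to be stated as one.
- **A plain exponent error.** Staff may always have intended to score against 1×10^10, in which case the remedy is a text correction. That is plausible, but the document does not say so, and an analyst following it would score against 1×10^8.
- **The consequence depends on the reading.** This stands. The threshold reading is permissive, while the literal window fails patients given the planned dose. Under neither does success show that the planned dose was reached.
- **The scenario figures are conditional.** This also stands. The yield range is a statement of capability, not a distribution, and lot yield need not equal dose given, since cells may be frozen for later use. The denominator is not fully settled either: feasibility is over enrolled patients, while the overview speaks of 40 infused patients. The early-stopping values also omit the separate hold requiring the first 3 and the next 3 patients to reach day +90 without DLT. Read literally, with all six infused, that hold is passed with probability 0.7^6 = 0.12 at 30% DLT and 0.8^6 = 0.26 at 20% DLT. It concerns toxicity, not dose, so it does not repair the endpoint.

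**Conclusion.** The concern holds and must be fixed. The 100-fold, non-overlapping mismatch is in the text and depends on no assumption. On the threshold reading, every lot in the stated yield range meets the dose criterion by a factor of at least 31 over its lower limit, and success among infused patients reduces to absence of DLT. Manufacturing and release failures still count against feasibility, because its denominator is enrolled patients. On the less likely literal window, the planned dose itself is a failure.

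The effect on the trial's course is illustrative: Bayesian-rule early stopping of about 0.001 to 0.04 in the threshold scenarios, against 0.92 to 0.999 with 1×10^10 ±20%. These ranges rest on assumed DLT rates, infusion shares and yield distributions. Yields may cluster near 1×10^10, so the second range is something to check, not a forecast. Confidence is high for the mismatch and for the endpoint not testing the planned dose; it is lower for how far the trial would move on the operating-characteristics table.

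**What to change.** The sponsor should confirm the intended target and use one figure in the success definition, the feasibility definition and the treatment plan. Presumably this is 1×10^10 ±20%, with doses below 0.8×10^10 scored as non-success. If a lower dose is clinically acceptable, that numeric minimum should be stated as the success threshold before any patient is scored. If 1×10^8 was truly meant, the treatment plan is what needs correcting.

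Before fixing the figure, check it against existing manufacturing yields. For a true success rate of 50%, the share of enrolled patients who must receive the target is 0.5 / (1 − DLT rate): 50% with no DLT, 0.5/0.9 = 56% with 10%, and 0.5/0.8 = 63% with 20%. At 1×10^10 ±20% this means 0.8×10^10 cells or more.

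The cost is a wording amendment and the yield check, with no extra patients or procedures. Sample size, boundaries and the operating-characteristics table stay as they are. The drawback is that fewer patients may count as successes at 1×10^10, and early stopping could become likely unless yields sit near the top of the range or a lower minimum is justified.

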Overall Response (CR+PR): We will assess overall response (CR+PR).

Infections: We will assess the rates of infection.

Criteria for Removal from Study:

1. **"Subjects" voluntary withdrawal from protocol.**
2. **Noncompliance of the patient with protocol requirements**
3. **After 5 years of treatment completion**
4. **Subject lost to follow-up**
5. **Decision by the investigators that withdrawing is in the subject's best interest**
6. **Pregnancy**
7. **Termination of the study by the investigator, IRB, or FDA**
8. **Unacceptable toxicity and other safety reasons- as defined by the stopping rules below.**
9. **Patients who experience DLT will not be eligible for retreatment.**

Toxicity Management, Stopping Rules and Study Termination

Only unexpected SAEs that are related to the activated autologous T cells would define a stopping rule.

Management of toxicity

Autoimmune toxicity associated with activated autologous T cells has been managed with a course of pharmacologic immunosuppression such as systemic corticosteroids.

Dose Limiting Toxicity

Dose limiting toxicity (DLT) is defined as any one or more of the following which occur after the T Cell Infusion:

1. Any Grade 3 or higher non-hematological adverse event other than fevers lasting less than 72 hours must will be considered DLT. Any prolonged grade 4 or higher hematologic toxicity (longer than 7 days) due to study treatment will be considered as DLT (CTC v4.03 CTCAE).
2. Allergic reaction or urticaria grade 3 or higher and deemed related to T cells (as determined using the Common Terminology Criteria for Adverse Events v4.03).
3. Grade 2 or greater autoimmune phenomena
4. Grade 4 or higher hematologic toxicity with the exception of any preexisting AE due to prior treatment or due to disease.

Stopping Rules

The statistical considerations section describes the primary stopping rule for the study, a rule which monitors patient success rate.

In addition, accrual to the study will be suspended to allow review with the institutional IRB if any death occurs among subjects who receive investigational agents due to the infusion of co-stimulated T-Cell product itself and not disease progression.

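### Dose-limiting toxicity is defined twice with different rules, so one patient can be both a primary-endpoint success and a DLT

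*Combined protocol and SAP*

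**What the plan says.** The Primary Endpoint section of the Statistical Considerations makes success depend on two things, the target cell dose and the absence of DLT. It then lists what counts as DLT for the trial:

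- Non-hematologic: "Any grade 4 or higher non-hematologic toxicity or grade 3 or 4 allergy/immunology toxicity".
- Allergic: "Allergic reaction or urticaria grade 3 or higher (CTC v4.03 CTCAE) by +90 days after T cell infusion".
- Autoimmune: grade 2 or greater.
- Hematologic: grade 4 or higher, not preexisting, and "deemed related to T cells and occurring by day +90 after T cell infusion".

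The Dose Limiting Toxicity section, under Toxicity Management, Stopping Rules and Study Termination, gives a second list, in which meeting any one item is enough:

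- Item 1, non-hematologic: "Any Grade 3 or higher non-hematological adverse event other than fevers lasting less than 72 hours must will be considered DLT".
- Item 1, hematologic: "Any prolonged grade 4 or higher hematologic toxicity (longer than 7 days) due to study treatment will be considered as DLT".
- Item 2: allergic reaction or urticaria of grade 3 or higher, if judged related to the T cells.
- Item 3: autoimmune, grade 2 or greater.
- Item 4: "Grade 4 or higher hematologic toxicity with the exception of any preexisting AE due to prior treatment or due to disease".

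The second list sets no end date. Neither list refers to the other.

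**The concern.** Both lists are current text, and each presents itself as the definition of DLT. They agree only on autoimmune events. The same term is used in five places:

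- the primary endpoint and the feasibility criterion (more than 50% of enrolled patients at target dose without DLT);
- through that endpoint, the Bayesian success-monitoring rule;
- the two pauses in which three patients must each reach day +90 without DLT before enrolment continues;
- removal from study;
- eligibility for retreatment at 6-12 months.

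If the counted event is not fixed, the success rate is not fixed either. The trial is open and single-arm and has no data safety monitoring board, and the study team itself assesses the monitoring rules. Two live definitions leave room for the choice to be made with the data in view.

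**Working it through.** **1. The plan's own figures.** Inputs from Safety Monitoring: Beta(1,1) prior, stop if Pr(success rate > 0.50 | data) < 0.025, minimum 6 patients, maximum 40. For each n, the boundary is the largest s with P(Beta(1+s, 1+n−s) > 0.5) < 0.025. All printed boundaries from 6 to 39 patients are reproduced. Exact binomial recursion, with a look after every patient from 6 to 39, gives:

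| True success rate | Early stop, printed | Early stop, recomputed |
|---|---|---|
| 0.3 | 0.833 | 0.8332 |
| 0.4 | 0.413 | 0.4131 |
| 0.5 | 0.108 | 0.1077 |
| 0.6 | 0.018 | 0.0178 |
| 0.7 | 0.002 | 0.0021 |

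The printed statistics are right for any given success rate. The open question is which success rate applies.

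**2. The two lists applied to the same patient.** All four patients below are assumed to have reached the target dose.

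| Patient | Primary Endpoint list | Dose Limiting Toxicity list |
|---|---|---|
| Grade 3 non-hematologic event, not allergic, immunologic, autoimmune or short fever | Success | DLT (item 1) |
| New grade 4 hematologic toxicity, unrelated to T cells and not due to disease or prior treatment | Success | DLT (item 4) |
| Related grade 4 hematologic toxicity first occurring after day +90 | Not a DLT | DLT |
| Grade 4 fever lasting under 72 hours | DLT | Excepted by item 1 |

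The last row runs the other way, so neither list contains the other, and taking the stricter list does not settle the matter.

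The second list also conflicts with itself. Item 1 requires more than 7 days and a study-treatment cause. Item 4 requires neither. Because one item is enough, item 4 makes those conditions of item 1 ineffective.

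**3. Size, under stated assumptions.** The documents give neither a grade 3 rate nor a dose-attainment rate. Assume that 5% of patients have a DLT under both lists (grade 4 or higher), that a further share g have grade 3 as their worst non-hematologic event, and that dose attainment a is independent of toxicity. Then:

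- success under the Primary Endpoint list = a × (1 − 0.05)
- success under the Dose Limiting Toxicity list = a × (1 − 0.05 − g)

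For example, 0.80 × 0.95 = 0.76, 0.80 × 0.75 = 0.60 and 0.80 × 0.65 = 0.52. Each rate goes through the same recursion. The feasibility criterion needs 21 or more successes in 40.

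| a | g counted as DLT | Success rate | Early stop | P(21+ of 40, not stopped) |
|---|---|---|---|---|
| 0.80 | none (Primary Endpoint list) | 0.76 | <0.001 | 0.999 |
| 0.80 | 0.05 | 0.72 | 0.001 | 0.996 |
| 0.80 | 0.10 | 0.68 | 0.003 | 0.984 |
| 0.80 | 0.20 | 0.60 | 0.018 | 0.864 |
| 0.80 | 0.30 | 0.52 | 0.077 | 0.532 |
| 0.70 | none (Primary Endpoint list) | 0.665 | 0.005 | 0.974 |
| 0.70 | 0.05 | 0.63 | 0.010 | 0.931 |
| 0.70 | 0.10 | 0.595 | 0.020 | 0.849 |
| 0.70 | 0.20 | 0.525 | 0.071 | 0.557 |
| 0.70 | 0.30 | 0.455 | 0.212 | 0.228 |

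**4. The enrolment pauses.** The chance that all of the first six patients are free of DLT is (1 − DLT rate)^6. Under the Primary Endpoint list it is 0.95^6 = 0.74. Under the other list it is 0.90^6 = 0.53 at g = 0.05, 0.75^6 = 0.18 at g = 0.20 and 0.65^6 = 0.08 at g = 0.30.

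**The case against.** The strongest reply is that placement settles the matter. One list sits under Primary Endpoint and would govern the endpoint, the boundaries and the enrolment pauses. The other sits under toxicity management and would govern removal and retreatment. The Stopping Rules section even sends the reader to the statistical section for the main rule. This is a natural reading, but nothing in the protocol states it, and both lists claim the same term without limit. It would also leave the internal conflict between items 1 and 4.

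Some points against the size do stand:

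- The Rationale's figure of over 80% of patients with infectious complications covers the disease course and any grade. It is not a 90-day grade 3 rate and cannot support the assumed 20-30%.
- At 80% attainment and a further 5-10% with grade 3 events, the feasibility result barely moves (0.996-0.984 against 0.999).
- The relatedness test for allergic reactions has little effect, because an unrelated grade 3 reaction is still caught by item 1.
- The missing day +90 limit matters for removal and retreatment. It does not alter success judged at day +90.
- The first enrolment pause forces the team to apply some definition early, which limits a late choice. It does not require that choice to be written down.

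Dose attainment is itself uncertain. The Primary Endpoint section prints the target as 1×10^8 and the treatment plan prints 1×10^10. That separate conflict must also be reconciled.

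**Conclusion.** The concern holds and must be fixed. The contradiction is in the text and needs no assumed rate: a patient at target dose can be a success under one list and a DLT under the other. The differences that reclassify patients are the non-hematologic grade threshold, the short-fever exception, and the hematologic attribution and time window.

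The effect on the result depends on how common the disputed events are. Under the independence and 5% assumptions above, a grade 3 share of 20-30% lowers the chance of meeting the feasibility criterion from 0.999 to 0.864-0.532 at 80% attainment, and from 0.974 to 0.557-0.228 at 70%. At 5-10%, that chance changes little at 80% attainment and moderately at 70%, but the enrolment pauses are still affected. These figures are illustrations, not estimates for this population.

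**What to change.** Replace the two lists with one DLT definition. It should give, for each class of toxicity, a single grade threshold, attribution rule, duration rule and list of exceptions, with one time window tied to the day +90 endpoint. If removal and retreatment need a longer window or a different event, give that event its own name. The primary endpoint, stopping rule, enrolment pauses, removal and retreatment sections should then refer to the definition and not restate it. The sponsor must decide which clinical thresholds apply; this review does not propose them.

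The cost is a wording amendment. The sample size, boundaries and operating-characteristics table stay as they are, and no extra data are collected. The cover page lists this version as terminated, so any report of patients already treated should state which list was used and give the success count under both.

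### Safety is half of the primary goal, but the supplied plan gives no DLT-rate estimate and no basis for a safety conclusion apart from a dose-plus-DLT composite

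*Combined protocol and SAP*

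**What the plan says.** All references are to the combined protocol and SAP.

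- **Goal** (Statistical Considerations, Overview): "The primary scientific goal is to determine the feasibility and safety of this procedure".
- **Primary endpoint** (Primary Endpoint): "Success will be defined as achievement of a target activated T-cell dose of" 1×10^8 ± 20%, together with absence of DLT. This is one binary outcome per patient.
- **Decision criterion** (same section): feasibility means reaching the target dose "without DLT in > 50% of patients enrolled". No matching criterion for safety is given.
- **Monitoring** (Safety Monitoring): "we will use a Bayesian sequential monitoring rule to monitor the primary endpoint of the study". Accrual stops if the posterior probability that the 90-day success rate exceeds 0.50 falls below 0.025, under a beta(1,1) prior and with at least 6 patients enrolled. The Stopping Rules section calls this the primary stopping rule.
- **Run-in** (Safety Monitoring): "We will enroll 3 patients and then wait till all 3 have reached +90 days without DLT before enrolling more patients". Three more patients then follow under the same condition.
- **Secondary Analyses**: immune reconstitution, overall response, and "Infections: We will assess the rates of infection". A DLT rate is not listed.
- **Other safety provisions**: a product-related death stops the study (Safety Monitoring) or suspends accrual for IRB review (Stopping Rules). Unexpected related SAEs define a stopping rule, with no count given. A halted study may resume only if a review finds that adverse events are not too frequent for this population and that no death was mainly due to the therapy.

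**The concern.** A composite of dose and DLT answers whether the procedure worked for a patient. It does not answer how often the product caused a DLT. A success count fixes only the number of failures, and each failure may be a missed dose, a DLT or both.

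The distinction matters here because missed doses may be common. Under Proposed Treatment/Study Plan the target is 1×10^10, the yield is described as "The process can generate 2.5×10^9 to 1×10^{10} cells", and "for patients who cannot achieve that dose, a lower dose of activated T cells that meets release criteria may be infused". A patient infused below target still carries DLT information, but against that target counts as a composite failure with or without a DLT. With the 1×10^8 target in Primary Endpoint, attainment is a different question.

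At stake is the safety half of the primary objective: the supplied text fixes no DLT estimate, denominator or interval on which to conclude.

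**Working it through.** **1. The plan's own figures.** For each n from 6 to 39, take the largest s with 1 − BetaCDF(0.5; 1+s, 1+n−s) < 0.025. For example, at n = 6 the value is 0.0078 for s = 0 and 0.0625 for s = 1, so the boundary is 0. All printed boundaries match. An exact binomial recursion with a look after every patient from 6 to 39 gives early-stopping probabilities of 0.833, 0.413, 0.108, 0.018 and 0.002 at true success 0.3 to 0.7, as printed. The arithmetic of the rule is sound; the issue is what it measures.

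**2. What a composite count says about DLTs.** No assumption about attainment is needed. Take 40 infused patients and Clopper-Pearson intervals.

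- 24 of 40 successes (60%, CI 43.3 to 75.1%) leaves 40 − 24 = 16 failures. DLTs can number from 0 (CI 0 to 8.8%) to 16 (16/40 = 40%, CI 24.9 to 56.7%).
- More than 50% of 40 means at least 21 successes, leaving 40 − 21 = 19 failures. Up to 19 DLTs (47.5%, CI 31.5 to 63.9%) are arithmetically compatible with the minimum positive result.

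**3. What the run-in adds.** Let q be the true DLT rate. Enrolment is held with probability 1 − (1−q)^6:

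| q | Run-in passed, (1−q)^6 | Held |
|---|---|---|
| 20% | 0.262 | 0.738 |
| 30% | 0.118 | 0.882 |
| 40% | 0.047 | 0.953 |

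After a clean run-in, the upper 95% limit for 0 of 6 is 1 − 0.025^(1/6) = 0.459.

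**4. What the composite rule adds against DLTs.** The documents do not give attainment, so it is assumed to range from 60% to 100% and to be independent of DLT. Success probability = attainment × (1 − q). Positive means at least 21 of 40 without an early stop. At q = 40%:

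| Attainment | Success | Rule stops, counted from patient 1 | Rule stops after a clean six | Positive after a clean six | Positive overall if a hold is final |
|---|---|---|---|---|---|
| 100% | 0.60 | 0.018 | 0.00002 | 0.980 | 0.046 |
| 90% | 0.54 | 0.055 | 0.0015 | 0.862 | 0.040 |
| 80% | 0.48 | 0.147 | 0.020 | 0.580 | 0.027 |
| 70% | 0.42 | 0.331 | 0.110 | 0.256 | 0.012 |
| 60% | 0.36 | 0.592 | 0.343 | 0.064 | 0.003 |

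The last column is 0.6^6 = 0.0467 times the column before it. The composite rule is weak against DLTs when attainment is high. At lower attainment it stops more often, but partly because of missed doses.

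**5. Precision of a separate DLT rate, 40 infused.** 4 DLTs: 10% (2.8 to 23.7%, width 20.9 points). 8 DLTs: 20% (9.1 to 35.6%, width 26.5 points).

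**6. Selection by the run-in.** If a hold is final, the first six of any continuing trial are DLT-free by construction. Ignoring later composite stops, the expected all-patient estimate is 34q/40 = 0.85q, so a true 20% reads as 17% on average.

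**The case against.** The strongest reply is that the plan does look at toxicity apart from the composite. The run-in is DLT-only. Read literally, its condition can never be met once a DLT has occurred, so a very toxic product would almost never reach 40 patients. Product-related death, unexpected related SAEs and the adverse-event review before a halted study resumes are further safeguards. The >50% criterion is labelled feasibility, so the plan nowhere says that passing it shows safety. Each patient's dose and DLT status must be recorded to score the composite, so no data are lost. The supplied text also begins as a protocol abstract, and investigators would probably tabulate DLTs anyway.

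Much of this stands. A reader might infer that the trial could readily declare the product safe with 19 DLTs in 40. The documents do not support that: 19 is an arithmetic maximum, a final hold makes a positive trial at high DLT rates very unlikely, and no safety claim is attached to the 50% threshold. Nor do the documents support saying that DLTs go unmonitored.

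The reply does not close the gap. The plan does not say whether a run-in hold is final. The run-in covers only six patients, and the remaining safeguards are event-based or qualitative and yield no DLT rate. The absence of a safety claim at 50% also leaves the safety question without any stated basis. An unplanned tabulation would have no denominator, window or interval fixed in advance.

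**Conclusion.** The concern holds as an omission in the supplied text. Safety is part of the primary goal, yet the only primary endpoint, the only decision criterion and the only rate-based stopping rule after the run-in rest on the composite, and no separate DLT rate is specified. The range of DLT rates compatible with one composite result (0 to 40% at 24 of 40) needs no assumption beyond 40 infused patients. The stopping and positive-result probabilities depend on assumed attainment and independence, and on whether a run-in hold is final.

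A reader might go on to infer that a DLT-only stopping boundary is required. The documents do not establish that: they state no acceptable DLT rate, and the run-in already gives substantial early protection if a hold is final. The gap is one of estimation and of the basis for the conclusion.

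Neither component is yet uniquely defined. The target dose is 1×10^10 under Proposed Treatment/Study Plan and 1×10^8 under Primary Endpoint. For non-hematologic toxicity, Primary Endpoint counts grade 4 or higher, whereas the Dose Limiting Toxicity section counts grade 3 or higher apart from short fevers. The two lists also differ on attribution and on the day +90 window.

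**What to change.** 1. Reconcile the two dose targets and the two DLT definitions before any rate is computed. The choice is for the sponsor.
2. Keep the composite and its monitoring rule unchanged.
3. Add two estimates, each with an exact 95% CI: target-dose attainment among enrolled patients, and the DLT rate by day +90 after the first infusion among infused patients.
4. State that the safety conclusion rests on the DLT rate and its interval, not on the composite exceeding 50%.
5. State whether a run-in hold is final. If it is, show patients 7 to 40 alongside the all-patient estimate, because the first six are DLT-free by selection.

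Items 3 and 4 are wording and a little extra analysis of data already collected, with no added patients or visits. Items 1 and 5 need substantive decisions, but the trial needs them in any case to classify a success and to run the run-in. The limit is precision: with 40 infused patients the DLT interval is about 21 to 27 points wide at rates of 10 to 20%, so the safety conclusion must be worded accordingly.
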